15. Female subjects of childbearing potential (including those who have undergone tubal ligation) must undergo a serum pregnancy test within 7 days before drug administration and record a negative result. After enrollment, serum or urine pregnancy test should be conducted on, Day 1 of every treatment cycle starting from Cycle 1, at EOT visit, and during Safety Follow-up Period. Unscheduled testing can be performed if there is an indication.
16. Urinalysis includes urine glucose, protein, ketone body, red blood cells, white blood cells, and urobilinogen.
17. Only required if subject has finding suggestive of active viral infection. Virological screening includes HIV, HBV (HBsAg, HBsAb, HBeAg, HBeAb, and HBcAb), HCV (HCV antibody), and CMV (CMV antibody). If HBsAg or HBcAb or CMV antibody is positive, CMV DNA or HBV DNA is also required to be assayed by PCR method. If CMV DNA or HBV DNA is negative, subjects may be enrolled and their CMV DNA or HBV DNA should be monitored every cycle. If HCV antibody is positive, HCV RNA is required to undergo PCR testing.
18. Patient enrolled to the control arm will not need to undergo PK sampling during the pre-surgery period of the study.
19. The 12-lead ECG indicators include PR interval, QRS interval, RR interval, QT/QTcF interval, and heart rate. Evaluation time points are shown in [Appendix 2](#). Unscheduled ECG or other cardiac examinations can be performed if clinically indicated.
20. De-identified tumor imaging with study number is to be transmitted to central vendor for image storage. Only the brain scan is required at the surgery time point, but other tumor imaging may be done if clinically indicated. Tumor imaging must be transmitted to the central vendor for image storage within 2 weeks after surgery.
21. AEs due to the protocol-required intervention (NGS testing) will be collected in the pre-screening phase. AEs will be collected from signing of the informed consent until 30 days after the last dose or initiation of new antitumor therapy. The relevant AEs will be followed up until they are recovered to the baseline status, already in a stable state as assessed by the investigator, start of new antitumor therapy, loss to follow-up, death, withdrawal of informed consent, the end of study, or it has been confirmed the AEs are unrelated to the study drug. SAEs are collected from the signing of the informed consent form until 30 days after the last dose or initiation of new antitumor therapy, whichever is earlier and until resolution regardless of relationship to study treatment.

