- ^{7.} Ophthalmologic assessments, including eye appearance, slit lamp examination, best corrected visual acuity, visual field, eye movement, pupil reflex, optical coherence tomography (OCT), and intraocular pressure will be performed during the Screening Period. If the subject has undergone the relevant examinations 60 days before the start of study treatment (C1D1), they need not be repeated. After the start of study drug administration, OCT will be performed at 6 weeks (± 1 week), then OCT, eye appearance, and slit lamp examinations will be performed every 12 weeks (± 1 week) from C4D1 and at the EOT visit. Other ophthalmic examinations are to be performed when clinically indicated. If the subject develops an ophthalmic AE related to HMPL-306, the frequency of the examination should be increased to once every cycle until the adverse event is relieved or stable.
- ^{8.} Hematology includes red blood cell count, hemoglobin, hematocrit, white blood cell count with differential and classifications (absolute neutrophil count, neutrophils % absolute lymphocyte count, lymphocytes %, absolute eosinophil count, eosinophils %, absolute monocyte count, monocytes %, absolute basophil count and basophils %), and platelet count. If abnormal or primitive immature cells are seen, they are also required to be recorded. Any additional routine blood tests during the study shall be arranged by the investigator as needed.
- ^{9.} These tests should be completed within 7 days before the start of treatment; if completed more than 7 days before the first dose, they must be repeated on C1D1 prior to dosing.
- ^{10.} Blood chemistry includes blood urea nitrogen, creatinine, sodium, potassium, magnesium, chloride, calcium, phosphorus, blood glucose, creatine phosphokinase, total bilirubin, direct bilirubin, indirect bilirubin, ALT, AST, ALP, LDH, total protein, and albumin.
- ^{11.} Fasting lipid panel includes total cholesterol, high-density lipoprotein, low-density lipoprotein, and triglycerides.
- ^{12.} Coagulation indicators include PT, aPTT, and INR.

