Visit			D1	D8	D15	D22	D28 (Day prior to surgery)		D1	D15	D1	D15	D1	Within 7 Days After the Last Dose	30 Days After the EOT Visit	Every 12 Weeks From EOT Visit
Visit Window (days)	--	-28 to -1	--	±1	±1	±1	--		±3	±3	±3	±3	±3	±3	±7	±14
Activities																
Pregnancy test ¹⁵		X	X				X		X		X		X	X	X	
Urinalysis ^{15,16}		X ¹¹					X		X		X		X			
Virological screening ¹⁷		X														
HbA1C		X ¹¹			X		X		X		X		X			
PK and PD assessments ¹⁸			Refer to Appendix 2													
12-lead ECG ^{7, 19}		X	Refer to Appendix 2													
ECHO/MUGA scan		X							X		X		C3D1 then Day 1 of every odd cycle (ie, C5D1, C7D1, etc.) (± 1 week)			
Tumor evaluation/imaging ²⁰		X						X within 2 weeks post op	Every 8 weeks from C1D1 during the first 24 (±1 week) weeks and every 12 (±2 weeks) weeks thereafter							X
Blood for gene mutation analysis		X							Refer to Appendix 2							
Study drug administration			HMPL-306 will be dosed at the RP2D						HMPL-306 will be dosed at the RP2D							
AEs ²¹	X	X	X	X	X	X	X	X	X	X	X	X	X	X	X	

AE = adverse event; ALP = alkaline phosphatase; ALT = alanine aminotransferase; aPTT = activated partial thromboplastin time; AST = aspartate aminotransferase; C = cycle; CMV = cytomegalovirus; D = day; DNA = deoxyribonucleic acid; ECG = electrocardiogram; ECHO = echocardiogram; ECOG = Eastern Cooperative Oncology Group; eCRF = electronic case report form; EOT = end of treatment; HBcAb = hepatitis B core antibody; HBsAb = hepatitis B e-antibody; HBsAg = hepatitis B e-antigen; HBsAb = hepatitis B surface antibody; HBsAg = hepatitis B s-antigen; HBV = hepatitis B virus; HCV = hepatitis C virus; HIV = human immunodeficiency virus; IDH = isocitrate dehydrogenase; INR = international normalized ratio; LDH = lactate dehydrogenase; MUGA = multigated acquisition; NGS = next-generation sequencing; PCR = polymerase chain reaction; PD = pharmacodynamic(s); PI = principal investigator; PK = pharmacokinetic(s); PT = prothrombin time; RNA = ribonucleic acid; RP2D = recommended phase 2 dose; SAE = serious adverse event.

1. If the subject chooses to continue treatment with HMPL-306, C1 will begin 4 to 8 weeks after surgery based on the clinical judgment of the PI.
2. Pre-screening informed consent is signed to obtain IDH mutational status report. Subjects who have already tested positive for IDH mutation may enter the Screening period directly.

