3. Written informed consent must be obtained before any study-related assessments or procedures are performed. However, before informed consent is obtained, if the examinations for standard treatment are performed within 28 days before the planned Day 1 of Cycle 1, they can be used to replace the examinations during the Screening Period without repeating the examinations, except for examinations that need to be performed 7 days before the start of the study drug administration, as specified in the table. For subjects enrolled in dose escalation, all screening examinations should be completed before study drug administration on Day -7. If there is dosing on the assessment day, all assessment examinations should be completed before the study drug administration, except 12-lead ECG, ECHO/MUGA scan, ophthalmologic examination, and efficacy assessments.
4. Subjects who have reports of positive IDH1 and/or IDH2 mutation tests may directly enter the Screening Period.
5. Medical history data include significant clinical disease or symptom, surgical history, history of malignancy (including date of diagnosis; classification and prognosis evaluation of the study disease, the treatment performed, and the outcome; and the tumor types and outcomes of any other previous malignancies), smoking history, history of alcohol consumption, history of drug abuse, and other medical-related history. Demographic information includes sex, race, and in some countries, date of birth.
6. Concomitant medications include any prescription and over-the-counter medications. During the Screening Period, all drugs used for the subject within 28 days prior to the start of study drug administration should be recorded in the eCRF. In subsequent visits, the drugs used by that period and within 30 days after termination of treatment should be recorded in the eCRF. Subsequent new antitumor treatment regimens during the Safety and Efficacy Follow-up Periods will also be recorded.
7. Physical examination, vital signs, weight, ECOG performance status score, weight measurement, laboratory evaluations, and ECG (unless otherwise stipulated) should be obtained within the scheduled visit date. During Cycle 1 and Cycle 2, all visits should be completed ± 1 day of the scheduled date unless otherwise stipulated. Starting from Cycle 3, unless otherwise stipulated, visits during treatment should be completed ± 3 days of the scheduled date. Unscheduled examinations may be performed if clinically indicated.

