8. Ophthalmologic assessments, including eye appearance, slit lamp examination, best corrected visual acuity, visual field, eye movement, pupil reflex, optical coherence tomography (OCT), and intraocular pressure will be performed during the Screening Period. If the subject has undergone the relevant examinations 60 days before the start of study treatment (C1D1), they need not be repeated. After the start of study drug administration, OCT will be performed at 6 weeks (± 1 week), then OCT, eye appearance, and slit lamp examinations will be performed every 12 weeks (± 1 week) from C4D1 and at the EOT visit. Other ophthalmic examinations are to be performed when clinically indicated. If the subject develops an ophthalmic AE related to HMPL 306, the frequency of the examination should be increased to once every cycle until the AE is relieved or stable.
9. Only for patients receiving HMPL-306.
10. Hematology includes red blood cell count, hemoglobin, hematocrit, white blood cell count with differential (neutrophils absolute neutrophil count and neutrophils %), lymphocytes [absolute lymphocyte count and lymphocytes %], eosinophils [absolute eosinophil count and eosinophils %], monocytes [absolute monocyte count and monocytes %], and basophils [absolute basophil count and basophils %], and platelet count. If abnormal or primitive immature cells are seen, they are also required to be recorded. Any additional routine blood tests during the study shall be arranged by the investigator as needed.
11. These tests should be completed within 7 days before the start of treatment; if completed more than 7 days before the first dose, they must be repeated on C1D1 prior to dosing.
12. Blood chemistry includes blood urea nitrogen, creatinine, sodium, potassium, magnesium, chloride, calcium, phosphorus, blood glucose, creatine phosphokinase, total bilirubin, direct bilirubin, indirect bilirubin, ALT, AST, ALP, LDH, total protein, and albumin.
13. Fasting lipid panel includes total cholesterol, high-density lipoprotein, low-density lipoprotein, and triglycerides.
14. Coagulation indicators include PT, aPTT, and INR.

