4.1.2 Part 2 (Dose Expansion)

In the dose expansion part, 4 cohorts of subjects will receive HMPL-306 to further evaluate the safety, tolerability, PK, PD, and preliminary efficacy of HMPL-306 at MTD or RP2D in approximately 95 subjects with locally advanced or metastatic solid tumors with IDH mutations.

There will be approximately 20 subjects (15 subjects in Cohort C-1) in each of the following cohorts:

- **Cohort A:** Cholangiocarcinoma
- **Cohort B:** Skeletal chondrosarcoma
- **Cohort C:** Low-grade glioma
 - **Cohort C-1:** Perioperative glioma
- **Cohort D:** Any other solid tumor harboring an IDH mutation

Depending on preliminary efficacy, safety signals, or operational feasibility, the Sponsor in conjunction with the SRC may decide to reduce or increase enrollment in these cohorts.

Study Treatment

Subjects will receive HMPL-306 at MTD or RP2D for 28 days in each cycle until disease progression, death, intolerable toxicity, the investigator's judgement that the subject can no longer benefit from the study treatment, withdrawal of consent, loss to follow-up, death, or the end of the study, whichever occurs first.

Cohort C-1: Perioperative Glioma

This cohort will serve as an open-label, window of opportunity study to assess the concentration of 2-HG in surgically resected tumors following pre-surgical treatment with HMPL-306 when compared to untreated tumors. This cohort will enroll 15 subjects with recurrent low-grade glioma with IDH1 or IDH2 mutations who are candidates for surgical resection. Subjects will be randomized in a 2:1 fashion to receive either open-label HMPL-306 at the RP2D for 4 weeks prior to surgery or no treatment (control) for 4 weeks prior to surgery.

All subjects enrolled to this cohort will undergo pre- and post-treatment procedures as outlined in Table 2. All subjects will have the option of receiving HMPL-306 following surgery. Subjects with no residual disease following surgery will be allowed to receive HMPL-306 for up to 1 year or until disease progression, whichever occurs first. If residual disease is evident following surgery, those subjects may receive HMPL-306 until disease progression.

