6.1.2 Screening Period

The Screening period is defined as the period from the Screening visit to before the first dose of HMPL-306 administration (up to 28 days prior to C1D1).

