6.1.3 Treatment Period

The treatment period is defined as the time from HMPL-306 administration on C1D1 to end-of-treatment (EOT) visit.

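### In Cohort C-1's HMPL-306 arm, Table 2 footnote 11 puts the repeat of out-of-date screening labs on C1D1, nominally 56 to 84 days after the first dose, instead of on pre-surgery D1

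*Protocol*

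**What the plan says.** Protocol Section 4.1.2 describes Cohort C-1 as a window-of-opportunity study in 15 subjects, "randomized in a 2:1 fashion to receive either open-label HMPL-306 at the RP2D for 4 weeks prior to surgery", or no treatment over the same 4 weeks. Table 2 (Section 1.3) and Appendix 2 start pre-surgery dosing on D1 and list that day separately from C1D1. Table 2 footnote 1 covers subjects who choose to go on with HMPL-306 after the operation: "C1 will begin 4 to 8 weeks after surgery based on the clinical judgment of the PI".

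Footnote 11 of Table 2 is attached to the screening entries for seven rows: hematology, blood chemistry, amylase and lipase, fasting lipids, coagulation, urinalysis and HbA1C. Its first clause asks for these tests in the 7 days before treatment starts. Its second clause covers the case where that was missed: "if completed more than 7 days before the first dose, they must be repeated on C1D1 prior to dosing".

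Footnote 3 of Table 2 lets standard-care tests from the previous 28 days stand in for screening tests, "except for examinations that need to be performed 7 days before the start of the study drug administration, as specified in the table". Table 1, for all other cohorts, carries the same fallback as footnote 9: "they must be repeated on C1D1 prior to dosing".

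**The concern.** The fallback names the wrong visit for the arm that is dosed before surgery. In that arm C1D1 comes after 28 days of drug, the operation and a recovery interval, and it does not occur at all if the subject stops at surgery. A site that has screening labs more than 7 days old and follows the footnote to the letter would give the first dose without repeating them.

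The pre-dose values have uses. Inclusion criteria 4 to 8 (Section 5.2) set limits on neutrophils, platelets, hemoglobin, transaminases, bilirubin, albumin, creatinine clearance and INR or aPTT, and give no time window of their own for these tests. Footnote 11 is what keeps the results current. Baseline values also feed the rule for reporting laboratory abnormalities as AEs (Section 8.7.4) and the grade-shift rule for dose modification (Section 7.4.4). Later scheduled samples are taken on treatment and cannot serve as a pre-dose check. Safety monitoring as a whole is not lost; the mandated pre-dose repeat is.

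**Working it through.** **Date of the named visit (HMPL-306 arm)**

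- First dose: pre-surgery D1 (Table 2, Appendix 2), so Day 1.
- Surgery: Table 2 labels D28 as the day before surgery, so surgery is Day 28 + 1 = Day 29.
- C1D1: 4 to 8 weeks after surgery (footnote 1), so Day 29 + 28 = Day 57 to Day 29 + 56 = Day 85.
- Interval from first dose: 57 − 1 = 56 days to 85 − 1 = 84 days.
- Applying the ±3-day visit window at C1D1: 56 − 3 = 53 to 84 + 3 = 87 days.

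**What Table 2 schedules for the seven footnoted tests**

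| Test | Pre-surgery D1 | First scheduled sample after D1 | Days after first dose | C1D1 |
|---|---|---|---|---|
| Hematology | no | D8 | 7 | yes |
| Blood chemistry | no | D8 | 7 | yes |
| Amylase and lipase | no | D8 | 7 | yes |
| Fasting lipids | no | D15 | 14 | yes |
| Coagulation | no | D15 | 14 | yes |
| HbA1C | no | D15 | 14 | yes |
| Urinalysis | no | D28 | 27 | yes |

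So 0 of 7 are marked on pre-surgery D1 and 7 of 7 on C1D1. The repeat ordered by footnote 11 would duplicate samples already due on C1D1 and leave the first-dose day empty. As a check on column alignment, the pregnancy test row is marked on pre-surgery D1, which agrees with the amendment summary's statement that a D1 test was added.

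**Comparison with Table 1.** There C1D1 is the day of first dose and 0 of the same 7 tests is otherwise marked on it. The same sentence therefore does its job in Table 1: it adds a pre-dose sample that would not otherwise exist.

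**Who is exposed.** 15 × 2/3 = 10 subjects in the HMPL-306 arm. Screening runs from Day −28 to Day −1, so labs 8 to 28 days old at first dose are possible, and only subjects with such labs reach the fallback clause. The documents give no rate for this, so the number affected lies anywhere from 0 to 10. For the other 15 − 10 = 5 subjects (controls), C1D1 is the first HMPL-306 dose if they opt in after surgery, and the footnote names the right day.

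**Other places where C1D1 stands for the first dose.** Table 2 footnote 8, on eye examinations done "60 days before the start of study treatment (C1D1), they need not be repeated", makes the same equation. Section 6.1.3 does too: "The treatment period is defined as the time from HMPL-306 administration on C1D1 to end-of-treatment (EOT) visit". The 28-day look-back in Table 2 footnote 3, the parenthesis in Section 6.1.2 and exclusion criterion 5 in Section 5.3 also count from C1D1. These are consistency points only; no loss of data was shown for them.

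**The case against.** The strongest reply is that this is a label slip whose intent can be recovered. Footnote 11 speaks of the start of treatment, the first dose and a repeat before dosing, and a repeat meant to precede dosing cannot sensibly fall 8 to 12 weeks after it. The body of the protocol uses C1D1 for the first dose, including Section 7.2.2.2 on drug dispensing. The first clause still sets the 7-day window. Footnote 3 and Section 5.1 withhold the 28-day allowance from tests that need the 7-day window, and footnotes 7 and 10 permit unscheduled tests. In addition, 10 of 15 is a ceiling, no subject entered the cohort, and no endpoint or analysis depends on the footnote.

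Much of this is fair. The slip looks carried over from Table 1 and was not a deliberate choice; Table 2 footnote 3 likewise still gives an instruction for dose-escalation subjects, who are not in this table. Ten is indeed the maximum. But Table 2 and Appendix 2 define C1D1 for this cohort as a separate, later day, and no other text moves the repeat to pre-surgery D1. The first clause of footnote 11 says what should happen, while the mandatory clause names the wrong visit. The exception in footnote 3 and Section 5.1 concerns standard-care tests done before consent, so it does not reach on-study screening labs that are 8 to 28 days old. Footnotes 7 and 10 allow a repeat but do not require one.

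**Conclusion.** The concern holds. For the HMPL-306 arm of Cohort C-1, footnote 11 as written places a mandatory pre-dose repeat nominally 56 to 84 days after the first dose (53 to 87 with the visit window), or nowhere if the subject does not continue after surgery. It applies to seven tests and to at most about 10 of the 15 planned subjects. The calendar assumes surgery on the day after D28, as Table 2 labels it.

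Two limits apply. The SAP (Sections 1 and 7) states that no subject was enrolled in any expansion cohort, so nothing in the trial's data is affected and this is a defect of the protocol as a plan. The protocol supplied is Amendment 2, whereas the SAP is based on Amendment 3, which was not available; whether the footnote was later corrected is unknown. The footnote should be corrected because it is an operative safety instruction that fails when followed literally.

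**What to change.** In Table 2 footnote 11, replace C1D1 with: *the day of first HMPL-306 dose (pre-surgery D1 in the HMPL-306 arm; C1D1 in the control arm)*.

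For consistency, make the matching change for the HMPL-306 arm wherever C1D1 stands for the first dose: Table 2 footnotes 3 and 8, the parenthesis in Section 6.1.2, Section 6.1.3 and exclusion criterion 5.

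The cost is one phrase, plus the matching labels. The 7-day requirement and the repeat are already in the protocol, so no procedure is added; the repeat simply moves to the day on which it is useful.

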2 INTRODUCTION

2.1 Study Rationale

2.1.1 Investigational Product

HMPL-306 is an innovative, small-molecule, orally available, highly selective, and very potent inhibitor of both isocitrate dehydrogenase (IDH) 1 mutants and IDH2 mutants.

2.1.2 Isocitrate Dehydrogenase

Isocitrate dehydrogenase is a rate-limiting enzyme in the tricarboxylic acid cycle participating in cellular energy metabolism and catalyzes the oxidative decarboxylation of isocitrate to generation of α -ketonyl acetylbenzoic acidglutarate (α -KG) and carbon dioxide. There are 3 isoforms of IDH enzymes in the human body, namely IDH1 located in cell cytoplasm, IDH2 in mitochondria, and IDH3 in mitochondria ([Wang 2013](#), [Yoshihara 2001](#)).

2.1.2.1 Mutations of IDH

IDH1 or IDH2 mutations or co-mutations have been associated with various tumors, including glioma, chondrosarcoma, and cholangiocarcinoma ([Kosmider 2010](#), [Marcucci 2010](#), [Pardananani 2010](#), [Yan 2009](#)). Mutations or co-mutations involving IDH1 and or IDH2 in tumor cells lead to abnormal functions, whereby mutant IDH converts α -KG into carcinogenic metabolite (R)-2-hydroxyglutarate (2-HG) ([Dang 2009](#), [Fathi 2012](#)). Accumulation of 2-HG in cells leads to series of epigenetic changes, including hypermethylation of deoxyribonucleic acid (DNA) and histone proteins, causing blockade of cell differentiation ([Chowdhury 2011](#), [Koivunen 2012](#), [Xu 2011](#)).

2.1.2.2 Mutations and Malignancies

Glioma is the most common intracranial malignant tumor, accounting for about 40% to 50% of all intracranial tumors. Studies have found that the incidence of IDH1 mutation in secondary glioma is more than 75% ([Parsons 2008](#)). At present, the IDH1 mutation inhibitors ivosidenib, BAY-1436032, and DS-1001 and the IDH1/IDH2 mutation inhibitor vorasidenib (AG-881) are being clinically evaluated for their therapeutic effect on gliomas with IDH1 mutation. In phase 1 clinical studies, the disease control rate of ivosidenib and vorasidenib on non-enhancing gliomas was 88% (n=35) ([Mellinghoff 2017](#)) and 91% (n=23), respectively ([Mellinghoff 2018](#)).

Chondrosarcoma is the most common bone sarcoma in adults and includes several subtypes: conventional, dedifferentiated, mesenchymal, and clear cell. Approximately 85% of all chondrosarcoma cases are of conventional subtype, and another 9% to 10% being dedifferentiated. For primary chondrosarcomas, surgery remains the primary method of treatment; however, there are no standard treatments for advanced disease ([Italiano 2013](#)). Chemotherapy is ineffective in conventional chondrosarcoma, and although chemotherapy options exist for dedifferentiated and mesenchymal subtypes, they provide minimal benefit. Recent studies have demonstrated that up to 65% of chondrosarcoma cases harbor an IDH1/IDH2 mutation. In a phase 1 study, ivosidenib, an IDH1 inhibitor, demonstrated a median progression-free survival (PFS) of 5.6 months (95% confidence interval [CI], 1.9-7.4 months) and a PFS rate at 6 months of 39.5% among 21 patients with advanced chondrosarcoma ([Tap 2020](#)).

Cholangiocarcinoma refers to malignant tumor originating in the bile duct epithelial cells, accounting for 10% to 15% of all primary liver cancers and less than 1% of all systemic tumors. Prognosis for intrahepatic cholangiocarcinoma is poor, with a 5-year survival rate of only 10%. It is more commonly seen in the 70- to 80-year-old demographics and has a slightly higher incidence rate in males (male:female ratio, 1.2-1.5:1.0). Intrahepatic cholangiocarcinoma arising from the intrahepatic biliary tree accounts for 10% to 20% of cholangiocarcinoma (Valle 2016). About 25% of patients with intrahepatic cholangiocarcinoma have IDH1 mutation (Lowery 2017). In the randomized, phase 3, ClarIDHy study, ivosidenib, an IDH1 inhibitor, demonstrated a median PFS of 2.7 months [95% CI, 1.6-3.6 months] for ivosidenib versus 1.4 months [95% CI, 1.4-2.5 months] for placebo (hazard ratio [HR], 0.47 [95% CI, 0.33-0.68]; $p < 0.0001$). The median overall survival (OS) was 10.8 months (95% CI, 7.7-17.6 months) for the ivosidenib group versus 9.7 months (95% CI, 4.8-12.1 months) for the placebo group (HR, 0.69 [95% CI, 0.44-1.10 months]; $p = 0.060$) (Abou-Alfa 2020).

HMPL-306 is a novel, small-molecule, orally available, highly selective, and potent inhibitor of mIDH. It demonstrated a remarkable inhibitory effect on 2-HG in tumor cells with any IDH mutations, and therefore, this phase 1, open-label study is planned to evaluate the safety, tolerability, pharmacokinetics (PK), pharmacodynamics (PD), and preliminary efficacy of HMPL-306 in patients with locally advanced or metastatic solid tumors with IDH mutations.

